There is one prior study of healthy pediatric patients that included 35 subjects (24 between ages 5-14 years and 11 between ages 15-18 years)[Etchell]. That study demonstrated that normal liver stiffness values were lower for healthy pediatric subjects than for healthy adult subjects (2.2 vs. 2.6 kPa). The authors also found a slight significant correlation between age and liver stiffness (r=0.38) but failed to demonstrate a difference in liver stiffness between subjects ≤14 years of age versus >14 years of age. While this prior study provides some information about normal liver stiffness in the pediatric population, it has key limitations. First, this study was performed with nonstandard multi-frequency MR elastography. One of the frequencies that was utilized (56 Hz) is close to the standard 60 Hz MR elastography utilized for clinical MRE, but differences in frequency utilized to measure tissue stiffness are known to influence liver stiffness measurements and thus normative data from this study may not apply to MR elastography performed with manufacturer standard technique. Second, the subjects imaged in this study were not fasting at the time of MR imaging. There are conflicting data regarding the effect of fasting (or lack thereof) on measured liver stiffness with some studies showing a stiffening effect of increased post-prandial splanchnic blood flow [Hines, Lemoine, Yin]. Third, while the subjects included in this study had no "known history of liver disease" MR fat fractions were not measured and serum liver function tests were not checked to confirm liver health. Finally, all examinations in this prior study were performed on a single manufacturer MR platform and at a single field strength, possibly limiting generalizability across other platforms.

MR elastography is a rapidly evolving technique and sequence improvements are constantly being developed. Additionally, new MRI techniques for assessment of diffuse liver disease are constantly being developed. At CCHMC only, additional imaging data will be acquired for exploratory aims related to these newer techniques.

4. STUDY DESIGN:

Study aims and hypotheses are as follows:

Primary aim/hypothesis – To determine normal liver stiffness values (and associated normal ranges) as measured by MR elastography for two pediatric age groups. We hypothesize that normal liver stiffness as measured by MR elastography will differ between the two pediatric age groups, increasing with increasing age.

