To achieve the primary aim, MR elastography will be performed in up to 104 healthy children, somewhat evenly divided (approximately 48 each) into two age groups (7-<12years, 12-<18years). Means, standard deviations and 95% confidence intervals for normal liver stiffness will be calculated for each age group and values will be compared across groups.

Multi-site secondary aims and hypotheses are as follows:

- To assess cross-platform variability in normal MRI liver stiffness values. We hypothesize that there will be no significant difference in mean normal liver stiffness values obtained on three different vendor platforms (GE, Philips, Siemens).
- 2. To assess for cross-field strength variability in normal MRI liver stiffness values. We hypothesize that there will be no significant difference in mean normal liver stiffness values obtained at 1.5T versus 3T.
- 3. To assess for sex-related (male vs. female) differences in normal MRI liver stiffness values. We hypothesize that there will be no sex-related differences in normal liver stiffness measured by MR elastography.

To achieve secondary aim #1, subject recruitment will be stratified across sites with approximately 32 subjects in each age group being imaged on each of the different vendor platforms (GE, Philips, Siemens). To achieve secondary aim #2, subject recruitment will be stratified across 1.5T and 3T magnets with approximately 48 subjects in each age group being imaged at each of the different field strengths. To achieve secondary aim #3, approximately equal numbers of male and female subjects will be recruited in each of the two age groups.

CCHMC exploratory aims and hypotheses are as follows:

1. To determine normal corrected T1 (cT1) values for two pediatric age groups. We hypothesize that there will be no significant difference in mean cT1 values between age groups or between field strengths.

Overall research strategy:

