We propose to conduct a multi-institutional study of normal liver stiffness values in pediatric subjects with no known history of liver disease. The requirement for multiple sites relates to the need to acquire normative stiffness values on each of the three major MRI vendor platforms to assess for unexpected cross-platform variability in liver stiffness. CCHMC has Philips MRI scanners (1.5 and 3T) equipped with MR elastography but does not have access to GE or Siemens MRI scanners in a research environment. Massachusetts General Hospital (MGH) has an elastography capable GE scanner (1.5T), Children's Hospital of Philadelphia (CHOP) has elastography-capable GE and Siemens scanners (3T), and Mallinckrodt Institute of Radiology (MIR) has an

elastography-capable Siemens scanner (1.5T). This human study protocol will be submitted for approval to the Institutional Review Board at CCHMC. CCHMC will serve as the lead site. CHOP, MGH and MIR may choose to submit to their IRB or to rely on the CCHMC IRB.

Power calculation relevant to SA1: Determine normal liver stiffness values (and associated normal ranges) as measured by MR elastography for three pediatric age groups: Based on the standard deviation of normal liver stiffness measurements in the study by Etchell et al. (SD=0.3 kPa) and the confidence intervals from a study of healthy adult livers by Lee et al. (95% CI ~±0.1 kPa), we calculate that a sample size of n=18 is needed in each group to achieve 2-sided 95% confidence intervals with a distance from the mean to the limits that is equal to 0.15 kPa for each group [Etchell, Lee]. This sample size also provides 80% power to detect an effect size (Cohen's d) of 0.67 between the two age groups. Given the prior study findings of a correlation between subject age and liver stiffness, we will recruit into two subject age groups (7-<12years, 12-<18 years). Based on prior published and unpublished MRI studies of "healthy volunteers" at CCHMC, we expect up to 25% of "healthy subjects" recruited for this study will have unsuspected liver disease manifest as abnormalities in liver function tests or liver fat fraction values greater than 5% by MRI proton density fat fraction (PDFF) (12). Therefore, we will increase recruitment targets by 25% over the levels required to achieve adequate statistical power. Thus, approximately 24 subjects will be recruited to each group at each field strength for a total study recruitment of n= up to 104.

MR imaging:

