All PDFF and MR elastography images will be processed both locally and centrally at a single site (CCHMC) by a single trained observer to ensure uniformity in post-processing technique. Post-processing will be performed as previously described with placement of single large regions of interest in the right hepatic lobe (12). Central MR elastography data will be post-processed using MRE Lab (Mayo Clinic, Rochester, MN) and PDFF data will be post-processed using Philips Intellispace (Philips Healthcare, Best, The Netherlands).

De-identified cT1 data acquired at CCHMC only will be sent to Perspectum Diagnostics for analysis.

Descriptive statistics will be utilized to describe the characteristics of each subject group (age, sex, scanner manufacturer, field strength). Normal liver stiffness for each age group will be summarized as mean ± std with range and 95% confidence interval also provided. Two sample t-test or one-way analysis of variance (ANOVA) will be used to assess for differences in liver stiffness between age groups and between different groups of categorical variables (sex, scanner manufacturer, field strength). The correlation between liver stiffness and continuous variables will be assessed by using Pearson on Spearman correlation coefficients as appropriate. Multiple linear regression models will be utilized to evaluate the association between liver stiffness and the predictor variables adjusting for all other covariates. Box plots will be generated to visually illustrate the results from the group comparisons mentioned above. All analyses will be performed using SAS version 9.4. A p-value less than 0.05 will be considered statistically significant for all inference testing.

10. FACILITIES and PERFORMANCE SITES:

Research blood draws will occur in the Schubert Research Clinic. All other study procedures will occur in the CCHMC Imaging Research Center (IRC).

11. POTENTIAL BENEFITS:

There are no direct benefits to study participants. This research, however, is critical for our understanding of normal MRE values in children which are relevant to the diagnosis of disease utilizing MRE. Therefore this research has potential future benefit to children with known or suspected liver disease.

12. POTENTIAL RISKS, DISCOMFORTS, INCONVENIENCES AND PRECAUTIONS:

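### Does Section 9 need to say which analysis decides the age hypothesis, and in what form age enters the regression?

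*Combined protocol and SAP*

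**What the plan says.** The primary aim in Section 4 is to establish normal stiffness values and ranges for children aged 7 to under 12 and 12 to under 18. The hypothesis attached to it reads: "We hypothesize that normal liver stiffness as measured by MR elastography will differ between the two pediatric age groups, increasing with increasing age". For this aim, Section 4 plans means, standard deviations and 95% confidence intervals per age group, and adds that "values will be compared across groups". The power paragraph in the same section explains the grouping: "Given the prior study findings of a correlation between subject age and liver stiffness, we will recruit into two subject age groups". It then gives the power for a standardised difference of 0.67 between the two groups: "This sample size also provides 80% power to detect an effect size".

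Section 9 names three kinds of inference that could bear on age:

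- Group comparison: "Two sample t-test or one-way analysis of variance (ANOVA) will be used to assess for differences in liver stiffness between age groups".
- Correlation: "The correlation between liver stiffness and continuous variables will be assessed by using Pearson on Spearman correlation coefficients as appropriate".
- Regression: "Multiple linear regression models will be utilized to evaluate the association between liver stiffness and the predictor variables adjusting for all other covariates".

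The same significance level, 0.05, applies to all three. None is labelled primary, and the regression predictors are not listed.

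**The concern.** The hypothesis can be read in two ways: as a difference between two groups, or as a steady rise with age. A t-test addresses the first. A correlation or a slope in years addresses the second. The two can part company, and Section 3 gives an example. The prior pediatric study found a "slight significant correlation between age and liver stiffness (r=0.38) but failed to demonstrate a difference in liver stiffness between subjects" on either side of age 14. If that pattern recurred here, Section 9 has no sentence saying whether the hypothesis was supported.

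Three things would be at stake:

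- **False positives.** With several candidate tests at 0.05 and none designated, the chance that at least one is significant under no age effect exceeds 5%.
- **The regression.** If an analyst entered age in years and age group together, each would be adjusted for the other and both would lose most of their power.
- **The normal ranges.** If only group results were shown, a trend inside a group would be hidden from readers who use that group's range.

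**Working it through.** **Reproducing the plan's figures.** Inputs from Section 4: SD 0.3 kPa, n = 18 for the confidence interval, target half-width 0.15 kPa, d = 0.67, 24 recruited per age group at each of two field strengths, and 25% expected exclusions.

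- Half-width: t(0.975, 17) × 0.3/√18 = 2.110 × 0.0707 = 0.149 kPa. This agrees with 0.15.
- Recruitment: 18/(1 − 0.25) = 24 per cell. Two field strengths give 48 recruited and 36 evaluable per age group.
- Power of the two-sided t-test at 36 per group: noncentrality 0.67 × √(36/2) = 2.84, power 80.05%. This agrees with 80%.
- At 18 per group: noncentrality 0.67 × √(18/2) = 2.01, power 49.7%. The 80% therefore belongs to the two age groups pooled over field strength, although the sentence follows n = 18.

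The powered analysis is thus a two-group t-test with 36 per group.

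**Does the choice of test change the answer?** These inputs are assumptions, not from the documents: ages uniform within each group (or peaked mid-group), normal errors, and sex, vendor and field strength unrelated to age and without effect. With 36 per group, d = 0.67, uniform ages, and a slope adjusted for sex, vendor and field strength (20,000 runs per row):

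| True shape | t-test | Slope in years | Disagree |
|---|---|---|---|
| Linear | 79.9% | 89.6% | 12.7% |
| Rise over 10–14 | 80.2% | 80.8% | 11.9% |
| Rise over 11–13 | 80.2% | 75.4% | 12.7% |
| Step at 12 | 79.9% | 67.4% | 17.0% |

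With mid-group peaked ages, disagreement is 8.9% to 11.0%. When the covariates are assigned at random instead of exactly balanced, the step case gives 20.4%. Neither test is uniformly stronger, so the plan has not picked a plainly inferior one.

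**How serious are the disagreements?** In the linear and step cases the non-significant test had a median p of about 0.09. It was below 0.20 in more than four of every five such trials, and the two estimates almost never had opposite signs.

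**False positives.** With no age effect, the t-test alone rejects in about 5% of trials. At least one of the t-test and the slope rejects in about 7.5%. At least one of four analyses (t-test, Pearson, regression on years, regression on groups) rejects in 8.9%.

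**Adjusted or unadjusted groups.** With a linear trend at r = 0.38, power is 82.5% for the t-test and 80.4% for the regression on groups. With a step it is 79.9% and 77.7%. Adjustment costs about 2 points.

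**Which test does the text point to?** Section 4 hypothesises a difference between the two groups, compares the two groups and powers the two groups. Section 9 links age groups to a t-test or ANOVA, and with two groups these are the same test. The opening of Section 9's statistical paragraph describes subjects by age, sex, manufacturer and field strength, and then treats the last three as categorical. Age is the only one of the four left for the planned correlations with continuous variables.

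**The case for a change.** The strongest reply is that inference is not designation. The hypothesis does mention a rise with age, the groups are justified by a correlation, and nothing in the text fixes the form of age in the regression. Two sentences would settle it at no cost in subjects. That is true as far as it goes: no sentence labels a primary test, and the omission about the regression is real.

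The supporting arguments carry less weight.

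- **Both age terms in one model.** With uniform ages the years term detects a linear trend in 35% of trials and the group term in 5%. For a step the figures are 5% and 28%. But Section 9 does not propose such a model, and an analyst who knows that one variable is a cut of the other would not fit it to test age.
- **Drift within a group.** If the rise is linear, the slope is 0.67 × 0.3/5.5 = 0.0365 kPa per year, where 5.5 years separates the group midpoints. The drift is then 0.18 kPa over the 5 years of the younger group and 0.22 kPa over the 6 years of the older. Under a step it is zero. This is a property of banded ranges, which are the stated aim. Naming a primary test would not remove it. A scatter plot would help readers, but that is a matter of presentation.
- **The prior study.** If r = 0.38 came from the 35 children alone, p is about 0.024, but Section 3 does not say so. That study split 24 against 11 at age 14. This one plans about 48 against 48 at age 12, so the earlier split result is a weak guide.

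**Conclusion.** The observation is accurate, but it does not call for a change. Followed as written, the plan yields sound estimates for each age group, a valid two-group test with 80% power at d = 0.67 and 36 evaluable per group, and on the natural reading a correlation with age. Four places in Sections 4 and 9 point to the group comparison as the test of the hypothesis, and correlation and regression read as supporting analyses. The primary product is estimation, which no choice of deciding test can alter.

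The residual exposure is a false-positive rate of up to 8.9% instead of 5%. It arises only if an analyst treats four analyses as interchangeable and claims support from any one of them. The disagreement rates of 9% to 20% rest on assumed age distributions and on d = 0.67, and they mostly reflect p-values just either side of 0.05. For a single-visit normative study with no treatment decision attached, labelling the t-test as primary and stating the form of age would be tidy drafting. Leaving it unsaid does not put a result at risk.

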14. DATA SAFETY & MONITORING: *

No formal data safety monitoring board will be appointed for this minimal risk study. Adverse events related to study procedures will be monitored by site Pls/study coordinators, recorded and reported to the overall study PI (CCHMC).

15. PRIVACY and CONFIDENTIALITY:

Each subject will be assigned a site-specific study ID number. Password-protected tables will be maintained at each study site that link the study ID number to the medical record number. This table will be maintained on a secure server or in a locked file cabinet, as appropriate. Identifying data will be saved in a password-protected

spreadsheets at the individual study sites. Any data that are extracted from the database and used for research will be subject to standard data protection practices. Only de-identified patient data (including study ID numbers) and de-identified imaging data will be transmitted from the individual study sites to CCHMC for central analysis. Only de-identified patient data will be shared with Perspectum Diagnostics.

